Appendix 18. France Appendix

This appendix applies to study sites located in France.

1. GCP Training

Prior to enrollment of any subjects, the investigator and any sub-investigators will complete the Pfizer-provided Good Clinical Practice training course ("Pfizer GCP Training") or training deemed equivalent by Pfizer. Any investigators who later join the study will complete the Pfizer GCP Training or equivalent before performing study-related duties. For studies of applicable duration, the investigator and sub-investigators will complete Pfizer GCP Training or equivalent every three years during the term of the study, or more often if there are significant changes to the ICH GCP guidelines or course materials.

2. Investigational Product

No subjects or third-party payers will be charged for investigational product.

3. Suspected Unexpected Serious Adverse Reactions (SUSARs)

Pursuant to a sponsor's safety reporting obligations under 21 CFR 312.32(c)(1), Pfizer will report to the Investigator all SUSARs. Investigator will receive and review SUSAR reports and report SUSARs to the responsible IRB/IEC according to institution's guidelines.

4. Collection of ethnic origin information

Information regarding ethnic origin will be collected in this study in compliance with the French Data Protection Authority (CNIL): Deliberation no. 2016-262 of 21 July 2016 amending the reference methodology for the processing of personal data conducted in connection with biomedical research (MR-001), § 2.2.3 Nature of the data.

Individuals participating in this study will consent that this information can be collected in the study before they enter the study.

The electronic Case Report Form (eCRF) will be used as the source file for ethnic origin in France. This information will not be recorded in the patient's medical records.

1. VERSION HISTORY

Table 1 Summary of Major Changes in SAP Amendments

Version/ Date	Associated Protocol Amendment	Rationale	Specific Changes
1 25 Jul 2018	N/A	N/A	N/A
2 23 Jan 2020	Protocol Amendment 5	Align with changes in study protocol amendment 5	
 Added responder analyses based on SCORAD and change from baseline analysis in SCORAD assessment of sleep loss in Section 2, Section 3.2.2 and Section 6.4.  Added endpoints percent change from baseline in total EASI score, Severity of Pruritus NRS and percentage body surface area in Section 3.2.2 and Section 6.4. Deleted endpoints response based on PtGA, DLQI, HADS and POEM in Section 3.3.1 and Section 6.5.  Updated the definition of baseline variables in Section 3.4. Updated the definition of a treatment emergent adverse event (TEAE) in Section 3.5.1, in alignment with the latest CaPS algorithm. Updated the criteria for inclusion into the PPAS in Section 4.2. Provided descriptions and scopes of the Week 16 Analysis and End of Study Analysis in Section 5 and Section 6. Updated the visit windows in Appendix 2 to

090177e1937d0b4e\Approved\Approved On: 18-May-2020 15:17 (GMT)

			
remove any gaps in the study period and provide the data cut definition of the Week 16 Analysis.
 
 • Replaced jump to reference analysis with a tipping point analysis, which is a more general approach and includes jump to reference as a special case. See sections 5.3.1 and Appendix 3. • Updated study treatment exposure definitions and summaries in Section 6.8.3. • Updated concomitant/background medications and non-drug treatment summaries in Section 6.8.4. • Additional minor changes to improve clarity and alignment with the protocol.
--	--	--	---

2. INTRODUCTION

This SAP provides the detailed methodology for summary and statistical analyses of the data collected in study B7451029. This document may modify the plans outlined in the protocol; however, any major modifications of the primary endpoint definition or its analysis will also be reflected in a protocol amendment.

2.1. Study Objectives

Study objectives and corresponding endpoints are provided in Table 2 below.

Table 2 Study Objectives and Endpoints

Primary Objective	Primary Endpoints
To compare the efficacy of 100 mg and 200 mg once daily (QD) of PF-04965842 versus placebo in adult subjects on background topical therapy with moderate to severe atopic dermatitis (AD).	
The following co-primary endpoints will be tested:
 
 • Response based on achieving the Investigator's Global Assessment (IGA) of clear (0) or almost clear (1) (on a 5-point scale) and a reduction from baseline (pre-dose Day 1) of ≥ 2 points at Week 12; • Response based on achieving the Eczema Area and Severity Index (EASI)-75 ($\geq 75\%$ improvement from baseline) at Week 12.

Secondary Objectives	Secondary Endpoints

To compare the efficacy of PF-04965842 versus dupilumab in terms of attaining a clinically significant improvement in the severity of pruritus for adult subjects on background topical therapy with moderate to severe AD;
	
Key Secondary Endpoints:
 
 Response based on achieving at least 4 points improvement in the severity of Pruritus Numerical Rating Scale (NRS) from baseline at Week 2.

To estimate the difference in efficacy measures between two doses of PF-04965842 and dupilumab for adult subjects on background topical therapy with moderate to severe AD;
	
 Response based on achieving the IGA of clear (0) or almost clear (1) (on a 5-point scale) and a reduction from baseline of ≥ 2 points at Week 16; Response based on achieving EASI-75 ($\geq 75\%$ improvement from baseline) at Week 16.

To estimate the effect of PF-04965842 on additional efficacy endpoints and patient-reported outcomes over time in adult subjects on background topical therapy with moderate to severe AD.
	
Secondary Efficacy Endpoints:
 
 Response based on achieving the IGA of clear (0) or almost clear (1) (on a 5-point scale) and ≥ 2-point reduction from baseline at all scheduled time points except Week 12 and Week 16; Response based on achieving a $\geq 75\%$ improvement in the EASI total score (EASI-75) at all scheduled time points except Week 12 and Week 16; Response based on achieving a $\geq 50\%$ and $\geq 90\%$ improvement in the EASI total score (EASI-50 and EASI-90) at all scheduled time points; Response based on achieving at least 4 points improvement in the severity of Pruritus NRS from baseline at all scheduled time points except Week 2; Time from baseline to achieve at least 4 points improvement in the severity of Pruritus NRS scale; Change from baseline in the percentage Body Surface Area (BSA) affected at all scheduled time points; Change from baseline of Patient Global Assessment (PtGA) at all scheduled time points; Change from baseline in Dermatology Life Quality Index (DLQI) at all scheduled time points; Change from baseline in EuroQol Quality of Life 5-Dimension 5-Level Scale (EQ-5D-5L) at all scheduled time points; Change from baseline in Hospital Anxiety and Depression Scale (HADS) at all scheduled time points; Change from baseline in Patient-Oriented Eczema Measure (POEM) at all scheduled time points;

090177e1937d0b4e\Approved\Approved On: 18-May-2020 15:17 (GMT)

	
 • Change from baseline in Pruritus and Symptoms Assessment for Atopic Dermatitis (PSAAD) total score at all scheduled time points; • Response based on a $\geq 50\%$ and $\geq 75\%$ improvement in SCORAD (SCORAD50, SCORAD75) from baseline at all scheduled time points; • Change from baseline at all scheduled time points in SCORAD subjective Visual Analogue Scale (VAS) assessments of sleep loss; • Steroid-free days by Week 16.
Safety Objectives	Safety Endpoints

To compare the safety and tolerability of 100 mg and 200 mg QD of PF-04965842 and dupilumab versus placebo in adult subjects on background topical therapy with moderate to severe AD;
 
To estimate the safety and tolerability of the two doses of PF-04965842 versus dupilumab, for adult subjects on background topical therapy with moderate to severe AD.
	
 • Incidence of treatment-emergent adverse event (AE)s; • Incidence of serious adverse event (SAE)s and AEs leading to discontinuation; • Incidence of clinical abnormalities and change from baseline in clinical laboratory values, electrocardiogram (ECG) measurements, and vital signs.
CCI	[Redacted]
[Redacted]	[Redacted]
CCI	[Redacted]

[figure not shown]
090177e1937d0b4e\Approved\Approved On: 18-May-2020 15:17 (GMT)

CCI
 
[REDACTED]
	
[REDACTED]

[REDACTED]
	
[REDACTED]

[REDACTED]
	
[REDACTED]

[REDACTED]
	
[REDACTED]

AD = Atopic dermatitis; AE = Adverse Event; BSA = Body Surface Area; DLQI = Dermatology Life Quality Index; EASI = Eczema Area and Severity Index; ECG = Electrocardiogram; EQ-5D-5L = EuroQol Quality of Life 5-Dimension 5-Level Scale; HADS = Hospital Anxiety and Depression Scale; CCI [REDACTED]; IGA = Investigator's Global Assessment; NRS = numerical rating scale; POEM = Patient-Oriented Eczema Measure; PSAAD = Pruritus and Symptoms Assessment for Atopic Dermatitis; PtGA = Patient Global Assessment; SAE = Serious Adverse Event. CCI [REDACTED]
	

2.2. Study Design

This is a randomized, double-blind, double-dummy, placebo-controlled, parallel-group, multi-center study to assess the efficacy and safety of PF-04965842 100 mg or 200 mg QD and dupilumab (as per label) compared with placebo in adult subjects on background topical therapy, with moderate to severe AD. This study will provide a direct comparison of both doses of PF-04965842 with dupilumab in terms of pruritus relief. This study will also provide data which will estimate the relative efficacy of both doses of PF-04965842 and dupilumab. The treatment duration is 20 weeks. A total of approximately 700 subjects will be enrolled from approximately 180 sites globally. A study design schematic is presented in [Figure 1](#).

Figure 1 Study Design Schematic

At Week 2 and Week 16, key secondary endpoints are measured.

At Week 12, primary endpoints are measured.

At Week 20, eligible subjects will enter the B7451015 long-term extension study; ineligible subjects will instead enter the 4-week off-treatment follow-up period in B7451029.

Note: Standardized background topical therapy must be used as per protocol guidelines throughout the study.

Subjects who continue to meet eligibility criteria at baseline will undergo Day 1 assessments and be randomized in a 4:4:4:1:1 ratio to receive 100 mg or 200 mg of PF-04965842 QD with dupilumab-matching placebo administered every other week, dupilumab 300 mg administered every other week (with a loading dose of 600 mg at baseline) with PF-04965842-matching placebo administered QD, or one of two sequences of PF-04965842-matching placebo administered QD with dupilumab-matching placebo administered every other week from Day 1, for 16 weeks followed by either 100 mg or 200 mg of PF-04965842 QD. Randomization will be administered using center-based permuted blocks. Investigators, subjects, and the sponsor study team will be blinded as to treatment group.

The total treatment period is 20 weeks. The first part of this treatment period consists of a 16-week randomized, double-blind, placebo-controlled, double-dummy treatment period with subjects receiving both injectable and oral investigational product. The randomization and double-blind will be maintained during the final 4 weeks of the treatment period, but subjects will only receive oral investigational product. At Week 16 in the treatment period, all subjects will cease injectable dupilumab or its matching placebo. Following Week 16, subjects previously receiving only placebo will receive PF-04965842 100 mg or 200 mg QD as per their randomized allocation. Subjects previously receiving PF-04965842 100 mg or 200 mg QD will continue their respective dose. Subjects previously receiving dupilumab will continue to take oral placebo.

Eligible subjects completing the entire 20-week treatment period of the study will have the option to enter a long-term extension (LTE) study, B7451015. Subjects discontinuing early from treatment, or who are otherwise ineligible for the LTE study, will undergo a 4-week follow-up period in study B7451029.

A full schedule of activities for the study is provided in [Appendix 8](#).

Study Treatments

- Orally administered 100 mg of PF-04965842 QD with dupilumab-matching placebo administered by subcutaneous injection every other week (two injections at baseline; to dummy the loading dose) from Day 1 to Week 16, followed by orally administered 100 mg of PF-04965842 QD until Week 20.
- Orally administered 200 mg of PF-04965842 QD with dupilumab-matching placebo administered by subcutaneous injection every other week (two injections at baseline; to dummy the loading dose) from Day 1 to Week 16, followed by orally administered 200 mg of PF-04965842 QD until Week 20.
- Dupilumab 300 mg administered every other week (with a loading dose of 600 mg at baseline) with PF-04965842-matching orally administered placebo QD from Day 1 to Week 16, followed by PF-04965842-matching orally administered placebo QD until Week 20.
- PF-04965842-matching orally administered placebo QD with dupilumab-matching subcutaneously injected placebo administered every other week (two injections at baseline; to dummy the loading dose) from Day 1 to Week 16 followed by orally administered 100 mg of PF-04965842 QD until Week 20.
- PF-04965842-matching orally administered placebo QD with dupilumab-matching subcutaneously injected placebo administered every other week (two injections at baseline; to dummy the loading dose) from Day 1 to Week 16 followed by orally administered 200 mg of PF-04965842 QD until Week 20.

Sample Size Determination

A total sample of 700 subjects, with 200 randomized to PF-04965842 200 mg QD, 200 subjects randomized to PF-04965842 100 mg QD, 200 subjects randomized to dupilumab and 50 subjects each randomized to two sequences of matching placebo for 16 weeks followed by (a) PF-04965842 100 mg QD and by (b) PF-04965842 200 mg QD (4:4:4:1:1 randomization) is planned. The two placebo sequences will be combined for purposes of analyses at all visits up to and including Week 16, which will result in a 2:2:2:1 randomization ratio. This will provide at least 96% power to detect a difference of at least 20% in IGA response rate between either dose of PF-04965842 and placebo, assuming the placebo response rate is 12% at Week 12. This will also provide at least 99% power to detect a difference of at least 30% in EASI-75 response rate between either dose of PF-04965842 and placebo, assuming the placebo response rate is 23% at Week 12.

Both co-primary endpoints must achieve statistical significance to meet the primary objective.

In addition, this sample size will also provide at least 92% power to detect a difference of at least 15% in the proportion of subjects with a ≥ 4 points improvement in the severity of Pruritus NRS between PF-04965842 and dupilumab, assuming the dupilumab response rate is 18% at Week 2.

The Type-I error rate is set at 5% (two-sided). The familywise Type-I error rate (for testing the co-primary and key secondary endpoints) will be strongly controlled at 5% using a closed-testing method based on a sequential, iterative Bonferroni-type approach. This is described in further detail in [Section 5.1](#).

The study has been sized to help gain sufficient safety data to be able to effectively evaluate the benefit-risk of PF-04965842 in conjunction with the other studies in the clinical development program, therefore the power for the co-primary endpoints is relatively high. This sample size will also help ensure adequate power is maintained for testing all the co-primary and key secondary endpoints for both doses of PF-04965842 via the multiple testing procedure.

3. ENDPOINTS AND BASELINE VARIABLES: DEFINITIONS AND CONVENTIONS

3.1. Primary Endpoints

The co-primary efficacy endpoints are:

- Response based on the IGA score of clear (0) or almost clear (1); and a reduction from baseline of ≥ 2 points at Week 12;
- Response based on the EASI $\geq 75\%$ improvement from baseline (EASI-75) at Week 12.

Detailed descriptions of how the IGA and the EASI scores are derived are provided in [Appendix 4](#) and [Appendix 5](#) respectively.

3.2. Secondary Endpoints

3.2.1. Key Secondary Efficacy Endpoints

The key secondary efficacy endpoints are:

- Response based on ≥ 4 points improvement from baseline in the pruritus NRS (NRS4) for severity at Week 2;
- Response based on achieving the IGA of clear (0) or almost clear (1) (on a 5-point scale) and a reduction from baseline of ≥ 2 points at Week 16;

- Response based on achieving EASI-75 ($\geq 75\%$ improvement from baseline) at Week 16.

Detailed descriptions of how the severity of Pruritus NRS is derived is provided in [Appendix 7](#).

3.2.2. Secondary Efficacy Endpoints

- Response based on achieving the IGA of clear (0) or almost clear (1) (on a 5-point scale) and ≥ 2 point reduction from baseline at all scheduled time points except Week 12 and Week 16;
- Response based on achieving a $\geq 75\%$ improvement in the EASI total score (EASI-75) at all scheduled time points except Week 12 and Week 16;
- Response based on achieving a $\geq 50\%$, $\geq 90\%$ and 100% improvement in the EASI total score (EASI-50, EASI-90 and EASI-100) at all scheduled time points;
- Percent change from baseline in total EASI score;
- Response based on achieving NRS4 at all scheduled time points except Week 2;
- Time from baseline to achieve NRS4;
- Percent Change from Baseline in Severity of Pruritus NRS each day from Days 2-15, Weeks 4, 8, 12 and 16;
- Change from baseline and Percent change from baseline in the percentage Body Surface Area (%BSA) affected at all scheduled time points;
- Steroid-free days by Week 16;
- Response based on a $\geq 50\%$ and $\geq 75\%$ improvement in SCORAD (SCORAD50, SCORAD75) from baseline at all scheduled time points. A detailed description of the derivation of the SCORAD score is provided in [Appendix 6](#);
- Percent change from baseline and change from baseline at all scheduled time points in the SCORAD total score;
- Percent change from baseline and change from baseline at all scheduled time points in SCORAD subjective assessments of sleep loss.

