	Time from baseline to achieve at least 4 points improvement in the severity of Pruritus NRS scale;
	Change from baseline in the percentage Body Surface Area (BSA) affected at all scheduled time points;
	Change from baseline of Patient Global Assessment (PtGA) at all scheduled time points;
	Change from baseline in Dermatology Life Quality Index (DLQI) at all scheduled time points;
	Change from baseline in EuroQol Quality of Life 5-Dimension 5-Level Scale (EQ-5D-5L) at all scheduled time points;

Change from baseline in Hospital Anxiety and Depression Scale (HADS) at all scheduled time points; Change from baseline in Patient-Oriented Eczema Measure (POEM) at all scheduled time points; Change from baseline in Pruritus and Symptoms Assessment for Atopic Dermatitis (PSAAD) total score at all scheduled time points; Response based on a \geq 50% and \geq 75% improvement in SCORAD (SCORAD50, SCORAD75) from baseline at all scheduled time points; Change from baseline at all scheduled time points in SCORAD subjective assessments of itch and sleep loss; Steroid-free days at Week 16. Safety Objectives **Safety Endpoints** To compare the safety Incidence of treatment-emergent adverse event (AE)s; and tolerability of Incidence of serious adverse event (SAE)s and AEs leading to discontinuation; 100 mg and 200 mg QD of PF-04965842 and Incidence of clinical abnormalities and change from baseline in clinical laboratory dupilumab versus values, electrocardiogram (ECG) measurements, and vital signs. placebo in adult subjects on background topical therapy with moderate to severe AD. To estimate the safety and tolerability of the two doses of PF-04965842 versus dupilumab, for adult subjects on background topical therapy with moderate to severe AD.

PF-04965842

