4.1. Inclusion Criteria

Subjects must meet all of the following inclusion criteria to be eligible for enrollment into the study:

- 1. Evidence of a personally signed and dated informed consent document indicating that the subject has been informed of all pertinent aspects of the study.
- 2. Male or female subjects aged 18 years or older at the time of informed consent.
- 3. Meet all the following atopic dermatitis criteria:
 - Clinical diagnosis of chronic atopic dermatitis (also known as atopic eczema) for at least 1 year prior to Day 1 and has confirmed atopic dermatitis at the screening and baseline visits according to Hanifin and Rajka criteria for AD¹⁷ (see Appendix 2).
 - Documented recent history (within 6 months before the screening visit) of inadequate response to treatment with medicated topical therapy for AD for at least 4 weeks, or who have required systemic therapies for control of their disease.

NOTE: Medicated topical therapy is defined as a topical product that contains an active pharmaceutical ingredient indicated for the treatment of AD (irrespective of whether it is an over-the-counter [OTC] or prescribed product).

- Moderate to severe AD (affected body surface area (BSA) ≥10%, IGA ≥3, EASI ≥16, and Pruritus NRS severity score ≥4 on the day of the baseline visit).
- 4. During the last 7 days prior to Day 1, for the treatment of AD, the subject must have used only non-medicated topical therapy (ie, emollient) without other active ingredients indicated to treat AD, or other additives which could affect AD (eg, hyaluronic acid, urea, ceramide or filaggrin degradation products) at least twice daily, with response to treatment remaining inadequate at baseline. The subject must also be willing and able to comply with standardized background topical therapy, as per protocol guidelines (Section 5.9.1), throughout the remainder of the study.

- 5. Willing and able to comply with scheduled visits, treatment plan, laboratory tests and other study procedures.
- 6. Female subjects who are of childbearing potential must not be intending to become pregnant, currently pregnant, or lactating. The following conditions apply:
 - a. Female subjects of childbearing potential must have a confirmed negative pregnancy test prior to randomization;

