7.8.3. SCORAD

SCORAD is a validated scoring index for atopic dermatitis, which combines extent (0-100), severity (0-18), and subjective symptoms (0-20) based on pruritus and sleep loss, each scored using a visual analog scale (0-10).

Extent (A, maximum score of 100%)

To determine extent of AD, rule of 9 is used to calculate body surface area affected by AD as a percentage of the whole body surface area. Body surface area as percentage of total body surface area for each body region is as follows:

- Head and neck 9%;
- Upper limbs 9% each;
- Lower limbs 18% each;

- Anterior trunk 18%;
- Back 18%;
- 1% for genitals.

The score for each body region is added up to determine the BSA affected by AD (A), which has a possible maximum score of 100%.

Severity (B, maximum score of 18)

A representative area of AD is selected. In this area, the severity of each of the following signs is assessed as none (0), mild (1), moderate (2) or severe (3).

- Erythema (reddening);
- Edema (swelling)/papulation;
- Oozing/crusting;
- Excoriation (scratch marks);
- Skin thickening (lichenification);
- Xerosis (dryness) (this is assessed in an area where there is no inflammation).

The severity scores are added together to give 'B' (maximum score of 18).

Subjective Symptoms (C, maximum score of 20)

Subjective symptoms, ie, itch and sleep loss, are each scored by the subject or caregiver using a visual analog scale (VAS) where "0" is no itch (or no sleep loss) and "10" is the worst imaginable itch (or sleep loss). The value for each should reflect the average on a 10 point scale for the last 3 days/nights. These scores are added to give 'C' (maximum score of 20).

SCORAD Total Score

The SCORAD for an individual is calculated by the formula: A/5 + 7B/2 + C (can range from 0 to 103).

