4.1. Full Analysis Set

The Full Analysis Set (FAS) is defined as all subjects who have been randomized and who have received at least one dose of treatment. Subject is assigned to the randomized treatment group regardless of actual treatment received. Analyses for binary endpoints that are defined based on a threshold of change from baseline (eg, NRS4) will also require the baseline value to be equal to or greater than that threshold (eg, for NRS4, the baseline value needs to be ≥ 4). For continuous endpoint change from baseline and percent change from baseline, subjects must have baseline value to be included in the analysis.

The number of subjects randomized and dispensed study medication but did not receive treatment will be reported.

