6.4.3. Continuous Endpoints

- Endpoints:
 - Weeks 2, 4, 8, 12 and 16 Change from Baseline and Percent Change from Baseline in % BSA, Total SCORAD score, SCORAD subjective assessments of sleep loss (VAS);
 - Weeks 2, 4, 8, 12 and 16 Percent Change from Baseline in Total EASI Score;
 - Percent Change from Baseline in Severity of Pruritus NRS each day from Days 2-15, Weeks 4, 8, 12 and 16;

- Summary: Change from baseline and/or percent change from baseline at each specified time points;
- Population: FAS;
- Statistical Method: MMRM in [Section 5.2.3](#);
- Missing Data: Observed Data.

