9. APPENDICES

Appendix 1. Summary of Clinical Efficacy Analyses

Efficacy Endpoints	Population	Analysis Method	Missing Data Imputation	Primary Analysis for Co-primary Endpoints
Week 12 IGA Response	FAS	CMH	NR	Yes
Week 12 IGA Response	PPAS	CMH	NR	No
Week 12 IGA Response	FAS	CMH	TP	No
Week 12 EASI-75 Response	FAS	CMH	NR	Yes
Week 12 EASI-75 Response	PPAS	CMH	NR	No
Week 12 EASI-75 Response	FAS	CMH	TP	No
Week 2 NRS4 for severity Response	FAS	CMH	NR	
Week 16 IGA Response	FAS	CMH	NR	
Week 16 EASI-75 Response	FAS	CMH	NR	
Days 2-15, Weeks 4, 8, 12 and 16 NRS4 for Severity Response	FAS	CMH	NR	
Time to NRS4 for severity	FAS	Time to Event		
Weeks 2, 4 and 8 IGA Response	FAS	CMH	NR	
Weeks 2, 4, 8, 12 and 16 EASI-50, EASI-90, EASI-100 Response	FAS	CMH	NR	
Weeks 2, 4 and 8 EASI-75 Response	FAS	CMH	NR	
Weeks 2, 4, 8, 12 and 16 Percent CFBL in Total EASI Score	FAS	MMRM	OD	
Days 2-15, Weeks 2, 4, 8, 12 and 16 Percent CFBL in NRS for severity	FAS	MMRM	OD	
Weeks 2, 4, 8, 12 and 16 Percent CFBL in %BSA	FAS	MMRM	OD	
Weeks 2, 4, 8, 12 and 16 CFBL and Percent CFBL in SCORAD Total Score	FAS	MMRM	OD	
Weeks 2, 4, 8, 12 and 16 SCORAD50 Response	FAS	CMH	NR	
Weeks 2, 4, 8, 12 and 16 SCORAD75 Response	FAS	CMH	NR	
Weeks 2, 4, 8, 12 and 16 CFBL and Percent CFBL in SCORAD (VAS) for sleep loss	FAS	MMRM	OD	
CFBL=Change from baseline; CMH=Cochran-Mantel-Haenszel; ANCOVA=Analysis of Covariance; MMRM=Mixed-effect Model Repeated Measures; NR=Non-Responder; OD=Observed Data; TP=Tipping Point				

090177e1937d0b4e\Approved\Approved On: 18-May-2020 15:17 (GMT)

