Appendix 6. Scoring Atopic Dermatitis (SCORAD)

SCORAD is a validated scoring index for atopic dermatitis, which combines extent (0-100), severity (0-18), and subjective symptoms (0-20) based on pruritus and sleep loss, each scored (0-10).

Extent (A, maximum score of 100%): To determine extent of AD, rule of 9 is used to calculate body surface area affected by AD as a percentage of the whole body surface area. Body surface area as percentage of total body surface area for each body region is as follows:

- Head and neck 9%;
- Upper limbs 9% each;
- Lower limbs 18% each;
- Anterior trunk 18%;
- Back 18%;
- 1% for genitals.

The score for each body region is added up to determine the BSA affected by AD (A), which has a possible maximum score of 100%.

Severity (B, maximum score of 18): A representative area of AD is selected. In this area, the severity of each of the following signs is assessed as none (0), mild (1), moderate (2) or severe (3).

- Erythema (reddening);
- Edema (swelling)/papulation;
- Oozing/crusting;
- Excoriation (scratch marks);
- Skin thickening (lichenification);
- Xerosis (dryness) (this is assessed in an area where there is no inflammation).

The severity scores are added together to give 'B' (maximum score of 18).

Subjective Symptoms (C, maximum score of 20): Subjective symptoms (ie, itch and sleep loss) are each scored by the subject using a visual analog scale (VAS) where “0” is no itch (or no sleep loss) and “10” is the worst imaginable itch (or sleep loss). The value for each should reflect the average on a 10 point scale for the last 3 days/nights. These scores are added to give 'C' (maximum score of 20).

SCORAD Total Score: The SCORAD for an individual is calculated by the formula: $A/5 + 7B/2 + C$ (can range from 0 to 103).

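### Percent change from baseline is planned for the SCORAD sleep-loss VAS, where a baseline of 0 is valid: the measure is undefined for those subjects and may be unstable near zero

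*SAP*

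**What the plan says.** SAP section 3.2.2 plans "Percent change from baseline and change from baseline at all scheduled time points in SCORAD subjective assessments of sleep loss". Section 6.4.3 repeats both forms for Weeks 2, 4, 8, 12 and 16, listing "Total SCORAD score, SCORAD subjective assessments of sleep loss (VAS") with the other change and percent-change endpoints, on the FAS, by MMRM, using observed data. Appendix 1 has the matching row: "CFBL and Percent CFBL in SCORAD (VAS) for sleep loss". The MMRM (section 5.2.3) reports LS means, LS mean differences, 95% confidence intervals and p-values, with the baseline value as a covariate.

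The protocol's endpoint table asks only for "Change from baseline at all scheduled time points in SCORAD subjective assessments of itch and sleep loss". The SAP's own objectives table (section 2.1) also lists only the change for sleep loss.

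Protocol section 7.8.3 describes the subjective part of SCORAD as "based on pruritus and sleep loss, each scored using a visual analog scale (0-10"). There and in SAP Appendix 6 the lower anchor, 0, means no itch or no sleep loss.

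Inclusion criterion 3 (protocol section 4.1) sets baseline minimums of BSA 10%, IGA 3, EASI 16 and Pruritus NRS 4. It sets none for sleep loss.

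For who enters these models, SAP section 4.1 says: "For continuous endpoint change from baseline and percent change from baseline, subjects must have baseline value to be included in the analysis". The same paragraph sets a baseline floor for binary endpoints defined by a threshold of change, such as NRS4. It sets none for percent change.

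**The concern.** Percent change divides by the baseline. For the other percent-change endpoints the entry criteria keep that divisor away from zero: directly for EASI, %BSA and Pruritus NRS, and indirectly for total SCORAD, since a subject with BSA of at least 10% and IGA of at least 3 cannot score zero. Sleep loss is the only one without such protection.

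Two things follow. A subject who reports no sleep loss at baseline satisfies the section 4.1 rule but has no percent change, and no rule says what to do; the handling would be left to programming. And for a subject just above zero, a modest worsening gives a very large positive value, while full resolution gives only -100%. A mean-based model with a linear baseline term does not remove variance that grows as the baseline approaches zero. At stake are the readability and precision of one reported secondary result, and an avoidable difference between the subjects behind the percent result and those behind the absolute result printed beside it.

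**Working it through.** **Stated figure.** The plan gives no sample size or power for this endpoint, so there is none to reproduce.

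**Inputs from the documents.** Scale 0 to 10 with 0 valid (protocol 7.8.3, SAP Appendix 6); baseline floors of 10% for BSA, 16 for EASI and 4 for NRS (protocol 4.1); 200 subjects per active arm and 100 on pooled placebo (SAP 2.2).

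**Step 1: the formula.** Percent change = 100 × (y − b)/b, where b is baseline and y the later score. At b = 0 it is undefined for every y.

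**Step 2: largest possible worsening.**
- NRS from 4: 100 × (10 − 4)/4 = +150%.
- EASI from 16: 100 × (72 − 16)/16 = +350%.
- BSA from 10%: 100 × (100 − 10)/10 = +900%.
- Sleep loss from 0.1, if recorded to 0.1: 100 × (10 − 0.1)/0.1 = +9900%.
- Sleep loss from 1, if recorded in whole points: 100 × (10 − 1)/1 = +900%.

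**Step 3: weight of one subject.** From 0.2 to 4.0 is 100 × 3.8/0.2 = +1900%. That moves a 100-subject arm mean by 1900/100 = 19 points and a 200-subject mean by 1900/200 = 9.5 points. From 0.5 to 5 is +900%, moving them by 9 and 4.5 points.

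**Step 4: illustration under assumptions.** The documents give no baseline distribution, recording resolution or variability for this item, so everything below is assumed. Power serves only as a gauge of precision.

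*Set A.* 200 active versus 100 placebo, true falls of 55% and 30%, residual SD 2, scores clipped to 0–10 and recorded to 0.1 unless stated.

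| Assumption | Power, percent change | Power, absolute change |
|---|---|---|
| 3% at 0, about 3.5% between 0 and 1 | about 44–47% | over 99% |
| About 6.5% between 0 and 1 | about 22% | about 98% or more |
| 10% at 0, 4.6% between 0 and 1 | 32% | 98% |
| First row, whole-point recording | 92% | about 98% or more |
| First row, noise SD shrinking with the square root of baseline | about 99% | about 98% or more |

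*Set B.* Same arm sizes, true falls of 50% and 25%, residual SD 2, recorded to 0.1, one-visit ANCOVA with baseline as covariate. Subjects lost are those with baseline 0, out of 300. The floor of 2 in the last column is illustrative and not from the documents.

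| At 0; between 0 and 1 | Lost | Placebo mean (median) | SE, percent | Power, percent | Power, absolute | Percent with baseline ≥2: SE, power |
|---|---|---|---|---|---|---|
| 1%; 0.3% | 3 | -23% (-25%) | 5.0 | 0.99 | 1.00 | 4.5, 1.00 |
| 5%; 3.4% | 15 | -16% (-25%) | 10.7 | 0.66 | 1.00 | 5.1, 0.99 |
| 10%; 8% | 31 | -2% (-25%) | 21.1 | 0.25 | 0.999 | 5.7, 0.97 |

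Percent change loses little if low baselines are rare, and much if they are fairly common, finely recorded and as noisy as higher ones. Absolute change is hardly affected in any of these cases.

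**The case against.** The gap may be only a line of wording. The low power figures need three conditions together: a noticeable share of subjects near zero, recording to 0.1, and noise as large at low baselines as at high ones. The documents fix none of these. With whole-point recording the largest worsening is +900%, the same bound as for BSA, and changing that one assumption lifts power from about 44–47% to 92%. The endpoint is not key and lies outside the multiplicity procedure; SAP section 5.2 says no significance will be claimed unless an exception is noted. Absolute change is planned alongside, and section 5.2 prescribes medians and quartiles in descriptive summaries. The SAP may also add to the protocol's plans (protocol section 9), so the protocol's silence on percent change is no error.

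Most of this stands and limits the size of the point. A reader might infer that the LS mean will be governed by a handful of good sleepers rather than by treatment. The documents do not support that, because it depends entirely on the unknown inputs. A reader might also infer that the percent and absolute results describe materially different populations. At 3% with baseline 0 the difference is 0.03 × 200 = 6 subjects in an active arm and 0.03 × 100 = 3 on placebo, which is small.

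The objection does not remove the undefined value at baseline 0, which arises at any recording resolution, or the absence of a rule for it. Nor is the measure purely descriptive: SAP section 6 presents p-values for each dose against placebo, and section 5.1 tests secondary endpoints at an unadjusted 5%.

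**Conclusion.** The point holds in a limited form. From the documents alone, the planned percent change is undefined at a valid baseline value that the inclusion rule admits, and it is strongly asymmetric near zero. The LS mean and interval may therefore be unstable. The size is open: under the assumed inputs, power runs from about 22% to over 99% for percent change, against about 98% or more for absolute change. These figures show sensitivity to baseline distribution, resolution and low-end noise; they do not predict this trial. The co-primary and key secondary endpoints are untouched, and the absolute change in sleep loss remains sound. The correction is still worth making before database release, because it costs almost nothing and keeps the zero-baseline rule from being chosen later.

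**What to change.** Delete percent change for the SCORAD sleep-loss VAS from SAP sections 3.2.2 and 6.4.3 and from its Appendix 1 row, and keep the absolute change, the only form listed in the protocol and SAP objectives tables.

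If a relative measure is wanted, pre-specify one of two forms:
- the ratio of mean change to mean baseline in each arm, rather than the mean of individual ratios; or
- individual percent change restricted to subjects at or above a stated minimum baseline, with the number excluded reported by arm.

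The cost is a short SAP edit. One descriptive relative measure is lost or restricted; no protocol endpoint, sample size or data collection changes.
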